The time to return to usual activity and the time to return to usual health are defined as the time in hours from the first dose of investigational product till the first one of 2 successive cases where the response is 'Yes' on respectively FLU-PRO additional question 7 and FLU-PRO additional question 9. Missing data within the series are allowed as long as within three successive planned recordings there is at most 1 recording missing.

In cases where there are no sufficient recordings of return to usual activity/health as defined above, the endpoint will be censored. Censoring will be at the first time of return to usual activity/health, if and only if after this observation there is no recording of difficulties in usual activities/health (ignoring missing recordings). If there are no recordings of return to usual

activity/health satisfying this criterion, the time of censoring is the time of the last diary entry + 24 hours. One exception is censoring at the Day 28 Visit (last study day for the subject). If the subject is not returned to usual activity/health on this day, the time of the last diary entry will be taken as the time of censoring.

Data will be presented using Kaplan-Meier curves and Kaplan-Meier estimates by treatment group, overall and by age group. For a comparison between treatment arms, the time to parameters will be analyzed using an accelerated failure time model. The model will use the parametric shape, selected based on the goodness of fit criterion (AIC), and may take a Weibull, log-logistic, lognormal, or gamma distribution. As baseline covariates the ordinal scale at baseline category (ICU, ward+O₂, ward-O₂) and the age category (≥ 18 - < 65 years, ≥ 65 - ≤ 85 years) will be included. If the data don't provide an acceptable model fit, alternatively a Cox proportional hazards model can be used (in case the hazards are proportional). In case a Cox proportional hazards model is used a Log-log plot of survival will be added to check the proportional hazard assumption. Additionally, the time to event data will be analyzed using the logrank test and Gehan-Wilcoxon method.

- **Time to significant reduction in influenza symptom severity.**

The time to significant reduction in influenza symptom severity (to mild or none for all influenza symptoms) is defined as time in hours from the first dose of investigational product until the first of 2 successive recordings in which the total score for each of the 2 recordings are lower or equal to 1 and all the domain scores are lower or equal to 1. The 2 successive recordings should have been done within 3 scheduled successive analysis timepoints (one missing in between is allowed).

Censoring will be done similar to the FLU-PRO time to return to usual activity and time to return to usual health as specified above.

Data will be presented using Kaplan-Meier curves and Kaplan-Meier estimates. For a comparison between treatment arms, the time to significant reduction in influenza symptom severity will be analyzed using an accelerated failure time model. The model will use the parametric shape, selected based on the goodness of fit criterion (AIC), and may take a Weibull, log-logistic, lognormal, or gamma distribution. As baseline covariate the age category (≥ 18 - < 65 years, ≥ 65 - ≤ 85 years) and baseline FLU-PRO total score will be included. If the data don't provide an acceptable model fit, alternatively a Cox proportional hazards model can be used (in case the hazards are proportional). In case a Cox proportional hazards model is used a Log-log plot of survival will be added to check the proportional hazard assumption. Additionally, the time to event data will be analyzed using the logrank test and Gehan-Wilcoxon method.

- **Proportion of patients with a significant reduction in influenza symptom severity.**

The proportion of subjects with a significant reduction in symptom severity (the total score for each of the 2 recordings are lower or equal to 1 and all the domain scores are lower or equal to 1) at each assessment will be tabulated.

4.2.7. *FLU-iiQTM Additional Daily Diary Items*

For the 9 additional daily diary items of FLU-PRO frequency distributions of the number (%) of subjects per additional FLU-PRO item and per response category will be shown at baseline and all post-baseline assessments, per treatment group.

4.2.8. *Correlation between viral load, viral titer and changes in clinical symptoms*

- **Correlation between the decline in viral load, the decline in viral titer and clinical symptoms**

The time to influenza A viral negativity (see definition in section 4.2.2) measured by viral load and viral titer will be correlated with the following clinical measures (see definitions in sections 4.2.3 and 4.2.6):

1. Time to resolution of symptoms (7 primary symptoms)
2. Time to resolution of symptoms (All symptoms)
3. Time to return to usual activity,
4. Time to return to usual health and
5. Time to significant reduction in influenza symptom severity

Scatter plots with smoother curve will be shown per treatment group for the above mentioned correlations. An additional table will be provided showing the spearman correlation coefficients.

- **Correlation between the viral load, viral titer and severity of clinical symptoms**

The post-baseline log₁₀ values of viral load and post-baseline log₁₀ values of viral titer from day 2 to day 7 will be correlated with the following severity of clinical symptoms (see definitions in sections 4.2.3 and 4.2.6):

1. Flu-iiQTM daily average symptom score post-baseline from day 2 to day 7
2. FLU-PRO total score post-baseline from day 2 to day 7

Scatter plots with smoother curve will be shown per treatment group for the above mentioned correlations. An additional table will be provided showing the spearman correlation coefficients.

- **Correlation between baseline viral load, baseline viral titer and clinical symptoms**

The baseline viral load and baseline viral titer will be correlated with the following clinical measures (see definitions in sections 4.2.3 and 4.2.6):

1. Time to resolution of symptoms (7 primary symptoms)
2. Time to resolution of symptoms (All symptoms)
3. Time to return to usual activity,
4. Time to return to usual health and
5. Time to significant reduction in influenza symptom severity

Scatter plots with smoother curve will be shown per treatment group for the above mentioned correlations. An additional table will be provided showing the spearman correlation coefficients.

4.2.9. *Other Outcomes*

▪ **Time to hospital discharge**

The time to hospital discharge will be calculated from the date of first study drug intake during hospitalization up to the date of discharge. Subjects still hospitalized at the end of the study (end date of hospitalization missing or after trial termination) will be censored at the trial termination date.

Data will be presented using Kaplan-Meier curves and Kaplan-Meier estimates. For a comparison between treatment arms, the time to hospital discharge in days will be analyzed using an accelerated failure time model. The model will use the parametric shape, selected based on the goodness of fit criterion (AIC), and may take a Weibull, log-logistic, lognormal, or gamma distribution. As baseline covariate the age category (≥ 18 - < 65 years, ≥ 65 - ≤ 85 years) will be included. If the data don't provide an acceptable model fit, alternatively a Cox proportional hazards model can be used (in case the hazards are proportional). In case a Cox proportional hazards model is used a Log-log plot of survival will be added to check the proportional hazard assumption. Additionally, the time to event data will be analyzed using the logrank test and the Gehan-Wilcoxon method.

4.3. **Safety**

All safety analyses will be done on the Safety Set. Analyses will be presented overall and by age category and by treatment group.

4.3.1. *Adverse events*

Pre-treatment AEs are defined as AEs that were reported or worsened after signing the ICF up to the start of study drug dosing. Treatment-emergent AEs (TEAE) are defined as AEs that were reported or worsened on or after the start of study drug dosing through the 28-day Safety Follow-up Visit.

Adverse events with a start date and time recorded will be allocated based on their start date and time. If there is no time recorded for the start of the adverse event the adverse event that occurred on or after the day of first treatment intake and not after the 28-day safety follow up visit will be considered as treatment-emergent. Only adverse events that occur before the day of first medication intake and after/on the day of signing ICF will be considered as pre-treatment.

In case the start date of an adverse event is partially or completely missing, a worst case allocation will be done using the available date and time information in the start and end date time of the adverse event (i.e. if possible based on the available information the adverse event will be allocated to the treatment phase and hospitalization sub period).

Adverse events

The variables related with adverse events are

- AE term (verbatim and MedDRA preferred term and system organ class)
- Onset date, End date and duration of AE
- Serious AE (Yes/No)
- Severity (Mild, Moderate, Severe, Life threatening)
- Action taken towards study treatment (Dose increased, Dose not changed, Dose reduced, Dose interrupted, Drug withdrawn)
- Relation to study treatment (Not related, Doubtful, Possible, Probable, Very likely)
- Outcome of AE
- AE leading to death (Yes/No)
- Concomitant treatment taken (Yes/No)
- Influenza-related complication (Yes/No)
- Anticipated AE (Yes/No)
- Required hospitalization/prolonged hospitalization (Yes/No)

The adverse events will be shown by MedDRA system organ class and preferred term, in order of descending overall frequency.

Summaries of TEAEs will be presented overall and by the severity of the AE and relationship to the study drug.

AEs leading to death, SAEs, AEs leading to dose interruption, and AEs leading to permanent discontinuation will be listed separately. All AEs through the Safety Follow-up Visit will be listed in an individual subject data listing, including pre-treatment AEs. Spontaneous adverse events reported after the Safety Follow-up Visit, including unresolved, ongoing adverse events will be listed as well.

Anticipated Events

An anticipated event is an AE (serious or non-serious) that commonly occurs as a consequence of the underlying disease or condition under investigation (disease related) or background regimen.

For the purposes of this study the following events will be considered anticipated events (see Appendix 1 for the classification of AEs into Anticipated Events and Anticipated Event Groups):

- Bacterial pneumonia
- Bronchitis
- Sinus infections
- Ear infections
- Worsening of asthma, asthma attack
- COPD exacerbation
- Complications of sickle cell disease, sickle cell crisis
- Complications of diabetes mellitus, diabetic ketoacidosis
- Acute respiratory distress syndrome (ARDS)

Frequency tabulations of anticipated events and anticipated event groups will be shown by treatment. The Incidence of Treatment Emergent anticipated events will

be compared between active treatment versus placebo by a one-sided Fisher exact test (significance level < 0.10).

▪ **Influenza-related complications**

Adverse Events reported as influenza-related complications will be tabulated overall and by category and adverse event. A listing showing the AEs reported as influenza-related complications and complication information will be made linking the information to the AE listing.

The categories of influenza related complications as recorded on the eCRF are:

- Bacterial Pneumonia
- Bacterial Superinfections,
- Respiratory Failure,
- Pulmonary Disease
- Cardiovascular and Cerebrovascular Disease.
- Other

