Assessment of influenza symptoms will be recorded by the subjects or the site staff/caregiver if the subject requires assistance on the ePRO device and analyzed as an efficacy measure of treatment. Resolution of influenza symptoms will be the time since the start of treatment of the first of 2 evaluations (over 24 hours) in which all symptom scores for each of the 2 assessments are none or mild for all 7 primary influenza symptoms (cough, sore throat, headache, nasal stuffiness, feverishness or chills, muscle or joint pain, and fatigue).

Impact of Influenza (Flu-iiQ™ Modules 2, 3, 4)

The impact of influenza on conduct of daily activities will be assessed in Module 2 of the Flu-iiQ™ (see [Attachment 3](#)), scored on a 4-point scale, as above, for each of 6 activities. Scores will be assessed twice daily, at the same times as when the symptom scale evaluation is performed, from study entry (Baseline, Day 1) through Day 14, and once daily from Day 15 through the Final Study Visit/Safety Follow-up Visit. Assessments along with the additional daily diary items (see [Attachment 4](#)) will be recorded on the ePRO device. Time to resumption of usual activities is the time at which all scores are reported as “no difficulty”.

Flu-PRO

The incidence and severity of symptoms (individual and composite) will be evaluated using the Flu-PRO questionnaire (see [Attachment 5](#)). Subjects will be asked to complete this questionnaire and additional daily diary items (see [Attachment 6](#)) on an ePRO device once daily (preferably in the evening) from study entry (Baseline, Day 1) through the Final Study Visit/Safety Follow-up Visit.

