11.6. Efficacy Analyses

The efficacy endpoints will be analyzed on the Full Analysis Set, consisting of all subjects who were randomized, treated and had a confirmed influenza A infection, and will be analyzed by drug received.

Descriptive statistics will be used for all efficacy endpoints and will be tabulated by treatment arm and by age cohort. No formal statistical hypothesis testing will be made.

Clinical outcomes

The incidence of influenza complications will be categorized in a hierarchical fashion. The overall category will consist of any complication, consisting of the following subcategories:

- bacterial pneumonia (culture confirmed where possible),
- other bacterial superinfections,
- respiratory failure,
- pulmonary disease: asthma, chronic obstructive pulmonary disease [COPD]),
- cardiovascular and cerebrovascular disease (eg, myocardial infarction, congestive heart failure [CHF], arrhythmia, stroke),
- post-baseline ICU admission,
- all-cause mortality

The incidences on Day 28 of each (sub) category will be analyzed using logistic regression; baseline characteristics that are predictive of the incidence of complications can be included based on goodness of fit criteria. Odds ratios and associated 95% CIs will be reported of active vs. control treatment.

The time to improvement of vital signs is defined as the time from first study treatment to when at least 4 of 5 symptoms (temperature, blood oxygen saturation, heart rate, SBP, respiration rate) are recovered, including normalization of temperature and blood oxygen saturation. Normalization is defined in Table 6. If subjects satisfy these criteria at entry they will be censored at that time (effectively they will be excluded from the analysis). The data will be presented using a Kaplan-Meier curve. The time to event data will be modeled using the accelerated failure time (if the data provide an acceptable model fit) or alternatively a Cox proportional hazards model (in case the hazards are proportional). Additionally, the time to event data will be analyzed using the Gehan-Wilcoxon method.

Table 6: Resolution Criteria for Vital Signs

Assessment	Resolution Criterion
Temperature	≤ 37.2 °C or ≤ 37.8 °C rectal or tympanic
Oxygen saturation	$\geq 92\%$ on room air without supplemental oxygen
Respiration rate	≤ 24 /min
Heart rate	≤ 100 /min
Systolic blood pressure	≥ 90 mmHg

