4.2.1. Clinical Outcomes

▪ **Incidence of influenza complications**

The incidence of influenza complications from first intake up to Day 28 will be categorized in a hierarchical fashion. The overall category will consist of any complication, consisting of the following subcategories

- bacterial pneumonia (culture confirmed where possible),
- other bacterial superinfections,
- respiratory failure,
- pulmonary disease: asthma, chronic obstructive pulmonary disease [COPD]),
- cardiovascular and cerebrovascular disease (eg, myocardial infarction, congestive heart failure [CHF], arrhythmia, stroke),
- post-baseline ICU admission,
- all-cause mortality

The occurrence (yes/no) of influenza complications from first intake up to Day 28 of each (sub) category will be analyzed using logistic regression with treatment group as covariate. In case influenza complications occur in both age categories, age category will also be added as a covariate and as an interaction with treatment group. If the model will not fit the age category and it's interaction will be removed. Odds ratios and associated 95% CIs will be reported of active vs. control treatment and – if available – of elderly patients vs. patients < 65 years.

▪ **Time to improvement of vital signs**

The time to improvement of vital signs is defined as the time (in hours) from first study treatment until the first assessment (actual date and time) of a successive series of 3 recordings (over 4 scheduled successive analysis time points, 1 missing time point is allowed) where at least 4 of 5 symptoms (temperature, blood oxygen saturation, heart rate, SBP, respiration rate) are recovered, with at least normalization of temperature and blood oxygen saturation. Normalization is defined in Table 6. If subjects satisfy these criteria at entry they will be censored at that time.

Only vital signs assessments assessed during hospitalization and up to Day 14 (during hospitalization) will be taken into account to determine time to improvement of vital signs. Assessments taken after hospital discharge or after day 14, whichever, comes first will not be taken into account. In case, there was more than one hospitalization period, only assessments of the first hospitalization period will be used.

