*On room air to be obtained from “Was oxygen saturation measured on room air?” on Vital Signs pages (SUPPVS.QVAL for SUPPVS.QNAM = ‘VSOXSMRA’)

▪ **Time to improvement of respiratory status**

Time to improvement of respiratory status is defined as the time (in hours) from first study treatment until the first assessment (actual date and time) of a successive series of 3 recordings (over 4 scheduled successive analysis time points, 1 missing time point is allowed) where normalization of blood oxygen saturation and respiration rate occurred (as defined in Table 6). Analysis performed will be analogous to the analysis for the time to improvement of vital signs. Note that the NEW Score at baseline should not be added as covariate in the models.

▪ **Clinical outcome on day 8**

The ordinal scale consists of 6 categories that are exhaustive, mutually exclusive, and ordered (Table 7). For all patients, the category at days 1 to 15 will be established as the worst category on that day. The clinical outcome on day 8 will be further analyzed.

The analysis of the clinical outcome on day 8 will be performed using a proportional odds model, modeling the common odds ratio of the improvement on the ordinal scale of active treatment versus control. Age category (≥ 18 - < 65 years, ≥ 65 - ≤ 85 years) and baseline clinical outcome category will be added to the model. In case the model will not fit, age category and subsequently baseline category will be deleted.

In case of missing data ($>10\%$), multiple imputation under the missing-at-random assumption will be employed as a sensitivity analysis. The Markov chain Monte Carlo (MCMC) method will be used to create a number of multiple imputation datasets with monotone missingness in the clinical outcomes (baseline until day 15). The number of imputation datasets will be the same as the percentage of missing data (White *et al.* 2011). A monotone ordinal logistic regression imputation model will be used to complete the remaining missing clinical outcomes. The models fitted using the multiple imputation datasets will be the same as the final model on the actual data. The results from the models on the multiple imputation datasets will be combined taking into account the between and within variation of the results.

Additionally a Wilcoxon–Mann–Whitney test will be performed to compare the clinical outcome on day 8 between the two treatments.

Table 7: Ordinal scale on Day 8

Outcome
Death

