Descriptive statistics and mean (SE) plots will be shown for the log₁₀ values of viral load and viral titer (qRT-PCR and viral culture) and the changes from baseline calculated in log₁₀ (vp/mL or TCID₅₀/mL).

- **Incidence of influenza A viral negativity by assessment**

The proportion of subjects with a negative viral load and a negative viral titer will be tabulated at each time point. In addition, per parameter and time point a logistic model with baseline viral load/viral titer and age category (≥ 18 - <65 years, ≥ 65 - ≤ 85 years) as covariates will be used to obtain the odds ratios (95% CI) for the comparison of the incidence of influenza A viral negativity of treatment versus placebo.

Stacked barcharts of the percentage of subjects per response category will be made by day and treatment for viral load and viral titer. The following response categories will be used:

- For viral load (log₁₀ vp/mL) measurements:
 - Target not detected (<2.05 log₁₀ vp/mL)

- Target detected ($<2.18 \log_{10} \text{ vp/mL}$)
- Quantifiable ($\geq 2.18 \log_{10} \text{ vp/mL}$)
- For viral titer ($\log_{10} \text{ TCID}_{50}/\text{mL}$) measurements:
 - Negative ($<0.75 \log_{10} \text{ TCID}_{50}/\text{mL}$)
 - Positive ($\geq 0.75 \log_{10} \text{ TCID}_{50}/\text{mL}$)

- **Time to influenza A viral negativity**

The time to influenza A viral negativity will be determined based on nasal MT swabs: a subject will be considered influenza A viral negative at the time point that the first confirmed negative nasal MT swab was recorded (in days) i.e. defined as time in days from start of treatment to first of assessments = 'negative' and the next assessed measurement is not = 'positive' (ignoring missings, i.e. if first 'negative' is last available assessment or if next assessed result after first 'negative' is also 'negative'). If this doesn't occur, a subject will be censored at the time of the last observed nonnegative swab + 1 day. Note that at baseline every subject is considered positive.

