Resolution of influenza symptoms is defined as the first of a successive series of 2 recordings in which all symptom scores for each of the 2 assessments are 0 or 1 for all 7 primary influenza symptoms of the Flu-iiQTM (cough, sore throat, headache, nasal congestion, feeling feverish, body aches or pains, and fatigue (tiredness)). If the first record of a successive series of 2 recordings of resolved influenza is before day 14 in the evening then the 2 successive recordings should have been done over 3 scheduled successive analysis timepoints, 1 missing timepoint is allowed. If the first record of a successive series of 2 recordings of resolved influenza is at or after the evening record of Day 14 then the 2 successive recordings should have been done within 2 scheduled successive analysis timepoints (no missing allowed).

In cases where there are no sufficient recordings of resolved influenza as defined above, the endpoint will be censored. Censoring will be at the first

time of resolved influenza symptoms, if and only if after this observation there is no recording of non-resolved influenza symptoms (ignoring missing recordings). If there are no recordings of resolved symptoms satisfying this criterion, the time of censoring is the first possible time point a diary entry could have been made after the last observation of the presence of influenza, which is 20:00 on the same day if the last observation was a morning diary entry (from 3:01 until 15:00), 8:00 the next day if the last entry was an evening diary (from 15:01 until 03:00) (Day 1 until Day 14, morning). If the last observation of the presence of influenza is on Day 14 in the evening or after day 14 then the time of censoring is the time of the last diary entry + 24 hours. One exception is censoring at the Day 28 Visit (last study day for the subject). If the subject is not recovered on this day, the time of the last diary entry will be taken as the time of censoring.

Subjects who discontinue the study before resolving influenza symptoms and have an adverse events being reported as influenza complication ongoing on the day of discontinuation of the study will be censored at day 28, 20:00.

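### The symptom time-to-event endpoints set no entry condition, so a subject already at none or mild at baseline who stays there counts as an event at the earliest possible time

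*SAP*

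**What the plan says.** **Symptom resolution (Flu-iiQ).** SAP 4.2.3: "Resolution of influenza symptoms is defined as the first of a successive series of 2 recordings in which all symptom scores" are 0 or 1 for all seven primary symptoms. Its main censoring rule covers incomplete evidence: "In cases where there are no sufficient recordings of resolved influenza as defined above, the endpoint will be censored". A further rule deals with subjects who discontinue with an ongoing complication. None covers a subject who meets the criterion on arrival. Protocol 9.4.1.1 and 11.6 define the endpoint in the same way and are equally silent.

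**FLU-PRO reduction.** SAP 4.2.6: "The time to significant reduction in influenza symptom severity (to mild or none for all influenza symptoms) is defined as time in hours" from first dose to the first of two successive recordings with the total score and every domain score at 1 or below. Despite the name, no fall from baseline is required.

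**Other endpoints.** For time to improvement of vital signs, SAP 4.2.1 says: "If subjects satisfy these criteria at entry they will be censored at that time". Protocol 11.6 spells out the consequence: "effectively they will be excluded from the analysis". Respiratory status follows suit: "Analysis performed will be analogous to the analysis for the time to improvement of vital signs". For time to viral negativity, SAP 4.2.2 fixes the starting state: "Note that at baseline every subject is considered positive".

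**The concern.** The sponsor saw the problem of subjects who are already recovered at entry and dealt with it for vital signs, but the symptom endpoints have no counterpart. Such subjects have nothing to resolve, so their event time carries no information about treatment. Counting them as the earliest events pulls the two arms together and adds spread. What is at stake is the treatment ratio with its 95% CI, and the Kaplan-Meier, log-rank and Gehan-Wilcoxon results for time to resolution, definitive resolution and FLU-PRO reduction.

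**Working it through.** The documents give no power, effect size or event count for these endpoints, so there is no planned figure to reproduce. The check is a comparison of texts followed by an illustration on assumed values.

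**1. Can such subjects be in the analysis?** Yes. Protocol 4.1 asks for hospitalisation for influenza and/or its complications and a positive PCR. Sections 4.1 and 4.2 contain no minimum symptom score. The FAS in SAP 3.2 requires randomisation, one dose and confirmed influenza A, with no symptom condition. Someone admitted mainly for a complication could score only none or mild on the seven items.

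**2. When do they count?** Only if two successive recordings stay at 0 or 1. If the first two post-baseline recordings do, the first of them is the event. A subject who worsens first counts later.

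**3. Do the model covariates deal with it?** Partly. The accelerated failure time (AFT) models include the baseline composite score (SAP 4.2.3) or the baseline FLU-PRO total score (SAP 4.2.6). Both are means and do not identify who already meets the criterion:

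- Flu-iiQ, one symptom at 3 and six at 0: 3/7 = 0.43, not resolved. All seven at 1: 7/7 = 1.0, resolved. The lower score belongs to the unresolved subject.
- FLU-PRO, three throat items at 2 and the other 29 items at 0: total 6/32 = 0.19, but the throat domain is 2, so the criterion is not met. All 32 items at 1: total 1.0, criterion met.

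The Kaplan-Meier, log-rank and Gehan-Wilcoxon analyses do not use these covariates.

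**4. Effect on the ratio.** Inputs from the documents: at most 90 subjects, allocated 2:1, so 60:30. Assumed: lognormal times, placebo median 100 h, true ratio R = 0.70, log-SD s = 0.5, no censoring, no covariates, and a share p in each arm with its event at 12 h.

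Mean log time in an arm is (1−p)·m + p·ln 12, so the ratio of geometric means becomes R^(1−p). The variance of log time in an arm is (1−p)s² + p(1−p)(m − ln 12)². Here m − ln 12 is ln(100/12) = 2.120 for placebo and ln(70/12) = 1.764 for active.

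For p = 20%:
- Ratio: 0.70^0.8 = 0.752.
- Placebo variance: 0.20 + 0.16 × 4.496 = 0.919.
- Active variance: 0.20 + 0.16 × 3.110 = 0.698.
- SE of the log ratio, kept: √(0.698/60 + 0.919/30) = 0.206.
- SE, excluded: √(0.25/48 + 0.25/24) = 0.125, with the ratio still 0.70.

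The same formulas give 0.713 at 5% and 0.725 at 10%. With R = 0.75 and s = 0.8 instead, a 20% share moves the ratio to 0.794, with SE 0.242 kept against 0.200 excluded.

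**5. Effect on the rank tests.** Simulation with 60:30, R = 0.70, s = 0.5, no censoring, and every such subject given the earliest time. Mean Gehan z:

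| Share | Kept | Excluded |
|---|---|---|
| 5% | 2.74 | 2.95 |
| 10% | 2.44 | 2.85 |
| 20% | 1.91 | 2.65 |

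Log-rank, which weights early events less, gives 2.25 kept against 2.51 excluded at 20%. Repeat runs under the same assumptions agree to within about 0.15. With s = 0.8 the Gehan z is 1.92 at a 0% share, and 1.23 kept against 1.68 excluded at 20%.

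**The case against.** The strongest reply is that this matters little. The primary endpoint is pharmacokinetic, no hypothesis is formally tested, and a lower z changes no decision. Flu-iiQ time to resolution is not in the protocol's numbered secondary list. The FLU-PRO reduction is, but the protocol itself describes it as reaching mild or none. The AFT models already carry the baseline score, and restricting the population drops subjects who enter mild and then worsen, whose course is informative. All of this stands as a limit on weight. It does not remove the gap, because the ratios and intervals will still be reported and read, and the covariates adjust only in part.

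Three stronger readings are tempting, and the documents do not support them:

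- A reader might infer that everyone who is mild at baseline counts as an early resolution. The definition needs two successive recordings that stay at 0 or 1, so the simulated timing is the worst case.
- A reader might infer bias toward one arm. Randomisation makes such subjects equally frequent on average. A chance imbalance is possible at 60:30, but no direction is expected.
- A reader might infer that the Spearman correlations in SAP 4.2.8 are diluted. Subjects with mild disease who also clear virus early could strengthen those correlations as easily as weaken them. Nothing here tests that.

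**Conclusion.** The concern holds in limited form. As written, the plan counts a subject who meets the symptom criterion at baseline, and stays there, as the earliest possible event, whereas for vital signs it in effect removes the corresponding subjects. The consequence is attenuation and lost precision in secondary or supportive endpoints. The size is unknown because the share is unknown. In the worst-case illustration the loss in mean Gehan z is 0.21 at 5%, 0.41 at 10% and 0.74 at 20%; log-rank loses 0.26 at 20%. These figures rest on assumed lognormal times, no censoring and a true ratio of 0.70, none of which comes from the documents. If no subject qualifies at baseline, nothing changes.

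**What to change.** Add to the SAP, before unblinding:

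- Analyse time to resolution and definitive resolution in FAS subjects with at least one of the seven primary symptoms scored 2 or 3 at baseline.
- Analyse time to significant FLU-PRO reduction in FAS subjects who do not meet the total and domain score criterion at baseline.
- Use the baseline definition in SAP 3.1.6, and state how a subject without a usable baseline questionnaire is handled.
- Report the number left out per arm, and keep the full-FAS analysis as a sensitivity analysis.

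Because the restriction depends only on baseline status, the comparison stays randomised. Defining it as a restriction also avoids having to choose between censoring and exclusion. The cost is SAP wording and slightly fewer subjects in these endpoints. Subjects who enter mild and later worsen would appear only in the sensitivity analysis.
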